9.5.1 List of Tables

- BCP response rates for infants by treatment group, study visit (v8 and v12), and cell subset
- Distribution of frequency of B cell among all infant participants by treatment group, study visit (v8 and v12), and cell subset
- Distribution of frequency of B cell among infant positive responders only by treatment group, study visit (v8 and v12), and cell subset

9.5.2 List of Figures

- Barcharts of infant BCP response rates and boxplots of frequency of B cell by treatment group, study visit (v8 and v12), and antigen
- Boxplots of frequency of B cell by treatment group, study visit (v1, v8, and v12), and antigen for placebo groups only without assessing positivity

9.6 Neutralizing Antibody (NAb)

Serum samples from all 38 infants in this trial against 6 viruses will be assessed in the TZM-bl neutralizing antibody assay to determine the kinetics, magnitude, and breadth of neutralizing activity.

Cell-free virus is pre-incubated with multiple dilutions of test sample prior to adding infection-susceptible target cells. Infection is recorded at each dilution of sample after a single round of infection. Titers of neutralizing antibodies are defined as the sample dilution that reduces the infection by 50% or 80%; the cut-off used may differ depending on assay conditions and the nonspecific activity of pre-immune samples and other normal test samples.

Neutralizing antibodies against tier 1 and tier 2 strains of HIV-1 will be measured in TZM-bl cells as a function of a reduction in Tat-induced luciferase reporter gene expression after a single round of infection with molecularly cloned, Env-pseudotyped viruses. TZM-bl (also called JC57BL-13) is a HeLa cell clone that was engineered to express CD4 and CCR5 and to contain integrated reporter genes for firefly luciferase and E. coli β-galactosidase under control of an HIV-1 long terminal repeat (LTR). The cells are highly permissive to infection by most strains of HIV, including primary HIV-1 isolates and molecularly cloned Env-pseudotyped viruses. DEAE-dextran (Diethylaminoethyl-Dextran) is used in the medium during neutralization assays to enhance infectivity. Expression of the reporter genes is induced in trans by viral Tat protein soon after infection. Luciferase activity is quantified by luminescence and is directly proportional to the number of infectious virus particles present in the initial inoculum. The assay is performed in 96-well culture plates for high throughput capacity. Use of a clonal cell population provides enhanced precision and uniformity. The assay has been formally optimized and validated for single-round infection with either uncloned or molecularly cloned Env-pseudotyped viruses produced by transfection in 293T cells.

All designated serum samples will be assayed against Tier 1 and Tier 2 strains of virus by starting with a 1:10 dilution of serum to obtain a neutralizing antibody titer. Titers will be defined as the serum dilution that reduces RLUs by 50% (or 80%) relative to the RLUs in virus control wells after subtraction of background.

Mandatory assays with visit 12 samples (2 weeks post final vaccination) will measure neutralization titers in TZM-bl cells against the Env-pseudotyped vaccine strain (CH0505TF) and a vaccine strain lineage virus that exhibits a tier 1A neutralization phenotype (CH0505.w4.3). Additional assays with the above mentioned viruses and vaccine strain lineage viruses that exhibit a tier 2 neutralization (CH0505s.G458Y.N279K.2/GnT1-, CH0505TF.gly4/GnT1-, phenotype CH0505s.G458Y.N279K.N280D.6/GnT1-, and CH505TF.gly4.S365P/GnT1-) will be performed in TZM-bl cells with visit 12 samples. Two indicator viruses, CH0505s.G458Y.N279K.2/GnT1and CH0505TF.gly4/GnT1-, were developed by [name] to detect precursors from the CH235 and CH103 bNAb lineages respectively, and are paired with mutant viruses CH0505s.G458Y.N279K.N280D.6/GnT1- and CH505TF.gly4.S365P/GnT1specificity of the nAb response. If a sample was positive for an indicator virus it wastested against the paired mutant virus; otherwise, the mutant virus was not tested. The magnitude of the precursor response is the fold difference in ID50 (or ID80) response, indicator vs. mutant virus.

Evaluated bNAb Lineages Binding		
Specificity	Indicator Virus	Knock out (mutant) Virus
CH235	CH0505s.G458Y.N279K.2/GnT1	CH0505s.G458Y.N279K.N280D.6 /GnT1
CH103	CH0505TF.gly4/GnT1-	CH505TF.gly4.S365P/GnT1-

The magnitude of the nAb response will be measured by the ID50 (ID80) neutralization titer which is defined is the serum dilution that reduced relative luminescence units (RLUs) by 50% and 80% relative to the RLUs in virus control wells (cells + virus only) after subtraction of background RLU (cells only). The response to a given virus/isolate is considered positive if the neutralization titer is above a pre-specified cutoff. The prespecified positivity cutoff for ID50 and ID80 is 10. The ID50 (ID80) titers for negative responders are censored at 5 (half of the positivity cutoff).

The magnitude of the precursor response is defined as the fold difference in ID50 (ID80) titer between the indicator virus and mutant virus. When the titer for the mutant virus is below the positivity cutoff, the precursor magnitude is right-censored and computed as the ID50 (ID80) titer for the indicator virus relative to the positivity cutoff. When the titer for the indicator virus is below the positivity cutoff, the sample is excluded from the analysis.

A positive precursor response is defined by a more than 3-fold difference in neutralizing antibody titer, indicator virus vs. mutant virus. This same threshold is applied to the fold-difference in ID50 titer and to the fold-difference in ID80 titer.

Given the right-censoring of precursor response magnitudes, we will use the Kaplan-Meier (KM) method to estimate the distribution of the precursor response magnitude and the proportion of participants with positive precursor response. A 95% confidence interval for this proportion will be calculated using the Greenwood formula. The KM-based estimated proportion is interpreted as the precursor response rate among participants with a positive response to the indicator virus. The KM-based reverse cumulative distribution describes the distribution of the magnitude of the precursor response among participants with a positive response to the indicator virus.

Groups 3 and 5 (20 mcg CH505TF and 5 mcg GLA-SE) and Groups 2, 4, 6, and 8 (placebo) were combined for analyses.

Tables show the response rates to each virus/isolate and corresponding 95% confidence intervals calculated by the Wilson score test method [1], as well as summary statistics among positive responders and both responders and non-responders. Precursor response rates estimated using the KM method and corresponding 95% confidence intervals calculated by Greenwood formula will also be presented. Comparisons of response rates between treatment arms (T1 vs. T3+ T5 vs. T7) for each virus will be summarized. Also, comparisons of ID50 and ID80 titers for each virus between treatment arms (T1 vs. T3+ T5 vs. T7) among all participants and among positive responders will also be presented.

Plots of neutralizing antibody titers show both response rates or precursor response and the distribution of magnitude of response to an individual virus or magnitude of precursor response. Positive responses are indicated by dots color-coded by treatment group, and negative responses by gray triangles. Data points for each participant (if any) are connected by a grey line. Box plots based upon data from only responders are superimposed on the distributions. The mid-line of the box denotes the median and the ends of the box denote the 25th and 75th percentiles. Whiskers extend to the extreme data points that are no more than 1.5 times the interquartile range or if no value meets this criterion, to the data extremes. Scatter plots of neutralizing antibody titers will show paired indicator and mutant virus titers within for each participant. Reverse CDF using Kaplan-Meier-based reverse cumulative distribution functions estimation by cell lineage will show the proportion of samples with fold change >= 3 (threshold for positivity) distribution of precursor response by cell lineage and treatment group over time for each lineage.

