9.6.1 List of Tables

- Response rate and corresponding 95% confidence intervals using the Wilson score method by isolate, inhibitory dilution, visit and treatment group (Placebo (C2+C4+C6+C8), T1, T3+ T5, T7).
- Precursor response rate and corresponding 95% confidence intervals using Greenwood formula by indicator/mutant pair, inhibitory dilution, visit and treatment group (Placebo (C2+C4+C6+C8), T1, T3+T5, T7).

- Summary statistics for NAb titers (minimum, 25th percentile, median, 75th percentile, maximum, mean, standard deviation) among all participants, by isolate, inhibitory dilution, visit, and treatment group (Placebo (C2+C4+C6+C8), T1, T3+T5, T7).
- Summary statistics for NAb titers (minimum, 25th percentile, median, 75th percentile, maximum, mean, standard deviation) among positive responders, by isolate, inhibitory dilution, visit, and treatment group (Placebo (C2+C4+C6+C8), T1, T3+ T5, T7).
- Summary statistics for nAb precursor response (fold difference, indicator vs. mutant virus) (minimum, 25th percentile, median, 75th percentile, maximum, mean, standard deviation) among all participants, by indicator/mutant pair, inhibitory dilution, visit, and treatment group (Placebo (C2+C4+C6+C8), T1, T3+ T5, T7).
- Summary statistics for nAb precursor response (fold difference, indicator vs. mutant virus) (minimum, 25th percentile, median, 75th percentile, maximum, mean, standard deviation) among all precursor positive participants, by indicator/mutant pair, inhibitory dilution, visit, and treatment group (Placebo (C2+C4+C6+C8), T1, T3+ T5, T7).
- Response rate comparison of treatment arms (T1 vs. T3+ T5 vs. T7).
- Precursor response rate comparison of treatment arms (T1 vs. T3+ T5 vs. T7).
- Response magnitude comparison of treatment arms among all participants (T1 vs. T3+ T5 vs. T7).
- Response magnitude comparison of treatment arms among positive responders (T1 vs. T3+ T5 vs. T7).

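### SAP 9.6 gives the nAb precursor rate only among indicator-positive infants, with a Greenwood interval that fails at 0% and 100%, and compares arms of at most five on it; no interval over all infants is listed

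*SAP*

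**What the plan says.** SAP 9.6 pairs each of two indicator viruses with a mutant. A sample negative to the indicator is not taken further: "otherwise, the mutant virus was not tested", and "When the titer for the indicator virus is below the positivity cutoff, the sample is excluded from the analysis". The precursor magnitude is the indicator-to-mutant fold difference in titer, and a response is positive above 3-fold. If the mutant titer is below the cutoff of 10, the fold is right-censored at the indicator titer divided by 10.

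The rate is estimated by Kaplan-Meier, and its meaning is stated: "The KM-based estimated proportion is interpreted as the precursor response rate among participants with a positive response to the indicator virus". For the interval: "A 95% confidence interval for this proportion will be calculated using the Greenwood formula". Neither a scale nor a rule for 0% or 100% is given.

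SAP 9.6.1 lists this rate by arm with Greenwood intervals, and a comparison of it across T1, T3+T5 and T7. For each virus separately it lists "Response rate and corresponding 95% confidence intervals using the Wilson score method by isolate, inhibitory dilution, visit and treatment group", which covers the indicator viruses and the pooled placebo group. It also lists fold summaries "among all participants, by indicator/mutant pair, inhibitory dilution, visit, and treatment group", although folds exist only for indicator-positive infants. No table gives a precursor rate over all infants.

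**The concern.** The precursor readout is the part of the nAb analysis that speaks to bnAb lineage specificity, under secondary endpoint 2. Three features weaken it. The interval fails at the ends of the scale, which arms of four or five infants can easily reach. A fold censored at or below 3 is unclassifiable, but Kaplan-Meier does not count it as an event, so it can lift the estimate to 100%. The arm comparison conditions on visit 12 indicator positivity, which vaccination can change, so the groups compared are not those that were randomised. At stake are the error bars on the precursor rate and the reading of the dose arms.

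**Working it through.** **Inputs.** T1 and T7 have 5 infants each (SAP 2.3); 4 are expected in Group 7 after 25% data loss (Protocol 6.1.2). T3+T5 has 18 enrolled (Protocol 6.1.1) and 13 after loss (Protocol 6.1.2). The documents give no infant precursor or indicator-positive rates, so I assume conditional precursor rates p of 30, 40 and 90% and indicator-positive rates q of 70 and 50%.

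**1. The plan's own figure.** With z² = 3.841, the Wilson upper limit for 0/n is z²/(n+z²) and the lower limit for n/n is n/(n+z²). For 0/4: 3.841/7.841 = 49.0%, which matches the 49% in Protocol 6.1.2. Likewise 4/4: 4/7.841 = 51.0%; 5/5: 5/8.841 = 56.6%; 0/5: 3.841/8.841 = 43.4%; 1/1: 1/4.841 = 20.7%; 2/2: 2/5.841 = 34.2%.

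**2. Greenwood at fold 3.** S = ∏(1 − d/n) and Var = S² Σ d/[n(n−d)], taken over observed folds of 3 or less.
- If there are none, the sum is empty and Var = 0, so the interval is 100–100. This holds for 1/1, 2/2, 4/4 and 5/5 alike.
- If the last infants at risk are all events, n − d = 0 and the interval is undefined. This happens whenever the estimate is 0%.
- In between, 3/4 gives 0.75 ± 1.96 × 0.2165 = 32.6% to 117.4% untransformed.

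**3. How often**, with no censoring and all infants indicator-positive. P(zero width) = pⁿ and P(undefined) = (1−p)ⁿ. Coverage is for the untransformed interval, counting undefined as a miss.

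| n | p | zero width | undefined | coverage |
|---|---|---|---|---|
| 4 | 30% | 0.8% | 24.0% | 68% |
| 4 | 40% | 2.6% | 13.0% | 84% |
| 4 | 90% | 65.6% | <0.1% | 34% |
| 5 | 30% | 0.2% | 16.8% | 80% |
| 5 | 40% | 1.0% | 7.8% | 84% |
| 5 | 90% | 59.0% | <0.1% | 40% |

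Among defined intervals only, coverage at 30/40/90% is 89/97/34% for n = 4 and 96/91/40% for n = 5. Wilson coverage is 92–99%. At n = 13, Greenwood coverage is 91–92% at 30–40%; at 90% it is 74%, with zero width in 0.9¹³ = 25%.

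**4. Random denominator.** With 4 infants, the chance that at least one is indicator-positive and the interval is zero-width or undefined is (1−q+qp)⁴ + (1−qp)⁴ − 2(1−q)⁴. The second term uses 1−q+q(1−p) = 1−qp. For q = 70%, p = 30%: 0.51⁴ + 0.79⁴ − 2 × 0.3⁴ = 0.068 + 0.390 − 0.016 = 44%. At p = 30/40/90% the results are 44/37/75% for q = 70% and 58/52/78% for q = 50%.

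**5. Censoring.** An indicator titer of 10 to 30 with a mutant titer below 10 is censored at fold 1 to 3. Take folds 2.0, 2.5 and 2.8 (censored) and 6 (observed). No event occurs by 3, so S = 1 and Var = 0: 100% (100–100). The bounds over the four infants run from 1/4 = 25% (Wilson 4.6–69.9) to 4/4 = 100% (51.0–100). If no larger fold existed, the estimate at 3 would be undetermined, and the SAP states no convention.

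**6. Arm comparison, hypothetical counts.** T1: 1 of 5 indicator-positive, and that one precursor-positive. T3+T5: 12 of 18 indicator-positive, 9 of those precursor-positive. The conditional rates are 1/1 = 100% and 9/12 = 75%. Over all infants they are 1/5 = 20% (3.6–62.4) and 9/18 = 50% (29.0–71.0), so the order reverses.

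**The case against.** The strongest reply is that the conditional rate is disclosed and coherent. A fold cannot be measured without an indicator response, and Kaplan-Meier is a reasonable choice for censored folds. That stands; a reader might infer a concealed denominator, but the SAP states it.

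A reader might also infer that the share of all infants with a precursor response cannot be recovered. That goes too far. The indicator-virus response rate times the Kaplan-Meier rate gives the point estimate wherever the curve is determined at 3. In an arm with no indicator-positive infant, the listed Wilson row already serves as the all-infant interval. What is missing is a listed rate, and an interval when some infants are indicator-positive.

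Secondary endpoint 2 names magnitude and breadth of neutralization rather than a precursor rate, and the per-virus tables deliver titers. That limits the consequence. The protocol also concedes insufficient power across regimens, so low power alone is no new point; the outcome-selected subsets are.

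The rates in the working are assumed. The only related result in the documents is that HVTN 115 adults had no CD4bs or V2 glycan precursors detected after the third dose (Protocol 4.1), so the 100% case is not the best supported. On a log-log scale, coverage among defined intervals at 30/40% rises to 99/97% for n = 4 and 100/99% for n = 5. The boundary failures remain on either scale.

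**Conclusion.** The concern holds, for a secondary readout. As written, the precursor rate can print 100% (100–100) or no interval in arms of at most five, where Wilson gives 51.0–100 for 4/4 and 0–49.0 for 0/4. Those two contrasts need no assumed rate, only uncensored folds for 0/4. Their frequency does depend on assumptions: with four indicator-positive infants and no censoring, zero-width and undefined together come to about 25%, 16% and 66% at true rates of 30, 40 and 90%. At 30–40% the failure is mostly an undefined interval; at 90% it is mostly zero width.

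A reader might infer that only T1 and T7 are affected. That is not supported either: at an assumed 90%, 13 infants still give 25% zero-width intervals and 74% coverage on the untransformed scale. The arm comparison is not one of randomised groups. The documents do not support extending the point to the primary endpoints (BAMA, B-cell phenotyping) or to the per-virus nAb tables.

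**What to change.** In SAP 9.6 and 9.6.1:
- Add a precursor response rate over all infants with a valid visit 12 indicator result, counting indicator-negative infants as non-responders, with the Wilson interval that SAP 8.4.1 already applies to crude response rates.
- Where a fold is censored at or below 3, show both bounds: counted negative and counted positive.
- Base any comparison of T1, T3+T5 and T7 on this rate and call it descriptive.
- Keep the Kaplan-Meier rate and curve as descriptive, with the number of indicator-positive infants beside them, and print no Greenwood interval at 0% or 100%.
- Editorial only: relabel the all-participant fold table as indicator-positive participants, and settle whether positivity means above 3-fold or at least 3-fold, since SAP 9.6 uses both.

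The cost is SAP wording and table shells; no new assay data are needed. The downside is that reported rates will look lower and some will become ranges.

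### The Kaplan-Meier precursor response rate in SAP 9.6 rests on an unstated independence assumption, and in small arms it can read 100% with a zero-width interval from one proven responder

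*SAP*

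**What the plan says.** All of this is in SAP 9.6, Neutralizing Antibody (NAb).

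- Cutoff: "The prespecified positivity cutoff for ID50 and ID80 is 10".
- Magnitude: "The magnitude of the precursor response is defined as the fold difference in ID50 (ID80) titer between the indicator virus and mutant virus".
- Exclusion: "When the titer for the indicator virus is below the positivity cutoff, the sample is excluded from the analysis".
- Censoring, for infants with a mutant titer under 10: "the precursor magnitude is right-censored and computed as the ID50 (ID80) titer for the indicator virus relative to the positivity cutoff".
- Responder: "A positive precursor response is defined by a more than 3-fold difference in neutralizing antibody titer, indicator virus vs. mutant virus".
- Estimator: "we will use the Kaplan-Meier (KM) method to estimate the distribution of the precursor response magnitude and the proportion of participants with positive precursor response", with a 95% Greenwood interval.

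The SAP interprets the resulting proportion as the precursor response rate among infants positive to the indicator virus. SAP 9.6.1 tabulates it by arm and compares T1, T3+T5 and T7. The read-out belongs to secondary endpoint 2. The SAP gives no independence condition, no bounds, no sensitivity analysis, and no rule for a Greenwood standard error of zero.

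**The concern.** Kaplan-Meier needs the censoring value to carry no information about the quantity being censored. Here the censoring value is indicator/10 and the quantity is indicator/mutant, so both contain the indicator titer. Whether weak neutralizers tend to have small folds is a biological question, and the method takes the answer to be no without saying so.

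The second issue needs no distributional argument. A mutant-negative infant is known to exceed 3-fold only if the indicator titer is above 30. Between 10 and 30, responder status cannot be determined. Serum is tested from a 1:10 dilution, so these are simply low-positive samples.

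The arms are small: 5 (T1), 18 (T3+T5), 5 (T7) and 10 (pooled placebo) enrolled. The protocol expects about 13 and 4 with data in T3+T5 and T7, and fewer remain once indicator-negative infants are dropped. What is at stake is a reported rate of 100% or 0%, with apparent certainty, resting on one infant. If titer levels differ between arms, the unresolved share and any bias can differ too, which would distort the between-arm comparison.

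**Working it through.** The documents give no numeric precursor rate, so there is no planned figure to reproduce. The check applies the rule as written.

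**Notation.** I = indicator titer, M = mutant titer, T = I/M. If M < 10, T is censored at C = I/10. The reported rate is S(3), the product of (1 − d/r) over observed folds up to 3, where d is the number of infants observed at that fold and r the number still at risk.

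**Which infants are resolved**

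- Proven positive: observed T > 3, or M < 10 and I/10 > 3, that is I > 30.
- Negative: observed T ≤ 3.
- Unresolved: M < 10 and 10 < I ≤ 30.

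**Worked examples (no distribution assumed).** Five infants have I = 12, 15, 20, 25, 28 and M < 10. They are censored at 1.2, 1.5, 2.0, 2.5, 2.8.

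- Sixth infant has fold 6.0. There is no observed fold at or below 3, so S(3) = 1. The Greenwood sum has no terms, so the SE is 0 and the interval is 100% to 100%. Bounds: 1/6 = 17% to 6/6 = 100%.
- Sixth infant has observed fold 2.9. It is the only infant still at risk at 2.9, so S(3) = 1 − 1/1 = 0. Bounds: 0/6 = 0% to 5/6 = 83%.
- One proven and 12 unresolved (n = 13): S(3) = 100%, SE 0. Bounds: 1/13 = 8% to 100%.
- One proven, five unresolved, one observed non-responder (n = 7). If the non-responder's fold is 1.2, all seven are at risk and S(3) = 6/7 = 86%. If it is 2.8 and the five unresolved are censored below that, two are at risk and S(3) = 1/2 = 50%. Bounds in both cases: 1/7 = 14% to 6/7 = 86%.

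**Size and direction of bias.** The titer distributions below are assumptions, all lognormal. Truth is the proportion with I/M > 3 among infants with I > 10. In the first four rows SDs are on the log10 scale and each simulated trial has 13 infants. The remaining rows are large-sample runs with indicator median 20 and SD 0.7 on the natural-log scale.

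| Assumed structure | Truth | Kaplan-Meier | Unresolved |
|---|---|---|---|
| I and M independent; I median 20, SD 0.4; M median 10, SD 0.3 | 46% | 55% | 29% |
| I and M independent; I median 20, SD 0.3; M median 8, SD 0.2 | 49% | 67% | 46% |
| As row 1, I median 60 | 75% | 78% | 10% |
| As row 1, I median 100 | 86% | 87% | 4% |
| Log-titer correlation 0.3; M median 8 | 48% | 57% | 44% |
| Log-titer correlation 0.9; M median 8 | 30% | 35% | 52% |
| Fold independent of I; fold median 2.5 | 40% | 40% | 45% |
| Fold falls as I rises | 29% | 20% | 49% |

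The excess is 9 and 18 points in the first two rows, 3 and 1 points at medians 60 and 100, none when fold is independent of I, and −9 points in the last row.

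**The case against.** The strongest reply has four parts.

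- A shared numerator does not by itself make censoring informative. When fold is unrelated to indicator titer, Kaplan-Meier is unbiased (40% against 40%), and the bias can also run downward. This stands. A reader might infer from the algebra that the estimate must be inflated; the documents give no titer distribution that would support that.
- The size depends on where titers fall. At indicator medians of 60 to 100 the excess is 1 to 3 points. This also stands.
- The obvious replacement, proven positives over all indicator-positives, is worse as a point estimate. It counts every unresolved infant as negative. It gave 32% against a truth of 46% and 29% against 49% in the first two scenarios of the table. In a 13-infant scenario with fold independent of indicator titer it gave 12% against 28%, where Kaplan-Meier gave 28%. This stands and shapes the fix.
- The SAP already plans scatterplots of paired indicator and mutant titers and Kaplan-Meier reverse distribution plots, no decision rule in the documents uses this rate, and the 0%/100% examples are constructed. This stands in part: the plots let a careful reader see unresolved infants, but the tabulated rate and interval do not show them. The 100% result is also not confined to contrived data. With assumed medians of 15 (indicator) and 5 (mutant) and natural-log SDs of 0.5, 34% of simulated arms of 13 indicator-positive infants gave 100%, and 19% did so with at most one proven responder.

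**Conclusion.** The concern holds in a limited form. The precursor rate is valid only if fold is independent of indicator titer, and the SAP neither states nor checks this. Separately, whatever the titer distribution, unresolved infants can leave a rate of 100% with a zero-width interval from one proven responder, or 0% with five infants unresolved. That part follows from the SAP's rules alone. The bias figures (from 9 points too low to about 18 too high) rest on assumed titers and show what is possible, not what to expect.

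Three stronger readings are not supported:

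- That every infant is censored. Only those with a mutant titer below 10 are.
- That unresolved infants are always counted as responders. Kaplan-Meier moves their weight to larger folds, so they count fully only when no observed fold at or below 3 lies at or above their censoring value. The 50% and 0% examples show otherwise.
- That Kaplan-Meier is necessarily biased upward.

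This should be changed before the analysis. It affects a derived summary of a secondary endpoint, and no power calculation depends on it.

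**What to change.** For each arm and lineage (CH235, CH103), and for ID50 and ID80 separately:

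1. Tabulate proven positive (observed fold > 3, or mutant < 10 and indicator > 30), negative (observed fold ≤ 3) and unresolved (mutant < 10 and indicator ≤ 30).
2. Report lower and upper bounds on the rate, counting all unresolved infants as negative and then as positive.
3. Replace the Greenwood interval with the range from the Wilson lower limit of the lower bound to the Wilson upper limit of the upper bound. The SAP already uses Wilson limits for other rates. With one proven and 12 unresolved infants, protocol Table 6-3 gives 1.4% for the lower limit of 1/13 and 100% for the upper limit of 13/13, so the range is 1.4% to 100%.
4. Keep Kaplan-Meier only as an estimate labelled as assuming fold independent of indicator titer. Add a bivariate lognormal model for indicator and mutant titers, with the mutant left-censored at 10, as a sensitivity analysis.
5. Do not use proven positives over n alone as the headline rate.
6. Settle the threshold. The definition requires more than 3-fold, while the description of the reverse distribution plot uses 3 or above.

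The cost is SAP wording and a few lines of code, with no new data. The downside is a wider reported range, because it shows the unresolved infants.
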